5.4. Concomitant Treatments

Investigator will try to minimize the concomitant medications for the patients during the trial duration.

Patients are not allowed to take any of the following medications during the study:

1. Intravesical instillation of hyaluronic acid, heparin, or GAG replacement therapy.
2. Anticholinergics: oxybutynine, tolterodine, solifenacin, propiverine.
3. β 3 agonist: mirabegron.
4. Tricyclic anti-depressants: imipramine, amitriptyline.
5. COX-2 inhibitor: such as celecoxib.
6. Narcotics or pain killers: such as morphine, codeine, tramadol.

6. ADVERSE EVENTS

6.1. Introduction

An adverse event is defined as a new medical condition or worsening of the existing condition following or during the trial medicinal exposure (including placebo). However, a deterioration of medical condition can be in doubt of either an adverse event or being due to the lack of efficacy of

the treatment. Situations as such should be considered as a lack of efficacy unless the sponsor or the investigators or the regulatory authorities state to the contrary.

All adverse events occurring during the study should be documented on Adverse Event Forms. One Adverse Event Form should be filled out for each adverse event. All items on the form should be completed and feedback to National Reporting System of Adverse Drug Reaction in Taiwan (ADR) as soon as possible. For serious adverse events, a preliminary Adverse Event Form must be returned to the ADR immediately (within 24 hours), with complete and/or new information submitted to the ADR as soon as it becomes known.

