2. OBJECTIVE AND ENDPOINTS

The objective of this study is to evaluate the efficacy and safety of LESW for the treatment of IC/BPS.

The primary and secondary endpoints are described as shown below:

(1) Primary End-point (1 month)

The efficacy of LESW will be evaluated for:

Net changes of the O’Leary-Sant symptom score from baseline to 1 month after the treatment day.

(2) Secondary end-points

Efficacy

The efficacy of LESW will be evaluated for:

- (1) Net changes of the following parameters from baseline to 1 month after the treatment day: VAS, functional bladder capacity (FBC), voiding frequency at daytime and voiding frequency at night time as recorded in 3-day voiding diary.
- (2) Global response assessment (GRA) of therapeutic result by the patient (categorized from -3 to +3, indicating markedly worse to markedly improved) at 3 months after the treatment day.
- (3) Net changes of the maximum flow rate, voided volume, and PVR from baseline to 1 month after the treatment day.

(4) Changes of urinary nerve growth factor and cytokines level from baseline to 1 month after treatment day.

Effectiveness of treatment was considered if the patient has an improved GRA by 2 scales at the end-point assessments.

Safety

(1) Local adverse event incidences (hematuria, miction pain, UTI, urinary retention). The severity of adverse event is categorized as indicated below:

Severity of AE	Description
Mild	Transient and easily tolerable, not affecting usual daily activities
Moderate	Causes patient's discomfort, interrupting usual daily activities
Severe	Causes considerable interference with daily activities and may be incapacitating or life-threatening

(2) Systemic Adverse Events:

Any systemic adverse event occurring after LESW will be asked to report and patients will be properly investigated and treated. The cause for systemic adverse event may be not related with LESW.

(3) Changes in physical examinations.

(4) Changes in blood pressure and other laboratory test results will be examined if patients have severe adverse events or physical examinations reveal abnormalities.

(3) Follow-up (3 months)

Efficacy

The efficacy of LESW will be evaluated for:

- (1) Net changes of the following parameters from baseline to 1 month after the treatment day: VAS, functional bladder capacity (FBC), voiding frequency at daytime and voiding frequency at night time as recorded in 3-day voiding diary.

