4.2. Inclusion Criteria

Patients must meet all the following criteria to be eligible to enter the trial:

- 4.2.1. Adults with age of 20 years old or above.
- 4.2.2. Patients with symptoms of unpleasant sensation (pain, pressure, discomfort) perceived to be related to the urinary bladder, associated with lower urinary tract symptoms of more than six months duration, in the absence of infection or other identifiable causes.
- 4.2.3. Patients has received cystoscopy and ruled out other bladder lesion.
- 4.2.4. Free of active urinary tract infection.
- 4.2.5. Free of bladder outlet obstruction on enrollment.
- 4.2.6. Free of overt neurogenic bladder dysfunction and limitation of ambulation.
- 4.2.7. Patient or his/her legally acceptable representative has signed the written informed consent form.

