4.3. Exclusion Criteria

- 4.3.1. Patients had received intravesical hyaluronic acid treatment in recent 3 months, or intravesical Botox injection in recent 12 months. Patients with severe cardiopulmonary disease and such as congestive heart failure, arrhythmia, poorly controlled hypertension, not able to receive regular follow-up.
- 4.3.2. Patients with bladder outlet obstruction on enrollment.
- 4.3.3. Patients with PVR >100 ml.
- 4.3.4. Patients with uncontrolled confirmed diagnosis of acute urinary tract infection.
- 4.3.5. Patients have laboratory abnormalities at screening including:
 - ALT > 3 x upper limit of normal range.
 - AST > 3 x upper limit of normal range.
- 4.3.6. Patients have abnormal serum creatinine level > 2 x upper limit of normal range.
- 4.3.7. Female patients who is pregnant, lactating, or with child-bearing potential without contraception.

- 4.3.8. Patients with any other serious disease considered by the investigator not in the condition to enter the trial.
- 4.3.9. Patients had received intravesical treatment for IC within recent 1 month.
- 4.3.10. Patients had participated investigational drug trial within 1 month before entering this study.
- 4.3.11. Patients with coagulopathy.

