7.2 Analysis

The statistical objective of this study is to demonstrate that the efficacy of LESW is superior to placebo with respect to the decreases of O'Leary-Sant symptom score, VAS, increase in functional bladder capacity and improvement in GRA. The safety profile of LESW or placebo for the either group of intravesical treatment of patients with IC/BPS will also be confirmed.

Primary Efficacy Endpoint

The efficacy of LESW treatment will be evaluated for:

(1) Net change of the O'Leary-Sant symptom score from baseline to 1 month after the treatment day.

Secondary Efficacy Endpoint

The efficacy of LESW will be evaluated for:

- (1)Net change of the following parameters from baseline to 1 month after the treatment day: Visual analog score (VAS) for pain (from 0 to 10), functional bladder capacity (FBC), voiding frequency at daytime and voiding frequency at night time as recorded in 3-day voiding diary.
- (2) Global response assessment (GRA) of satisfaction by the patient (categorized into -3, -2, -1, 0, 1, 2, 3, indicating markedly worse to markedly improved) at 1 month after the treatment day. An improvement of GRA by 2 scales at 1 month is considered effective.
- (3) Net changes of the maximum flow rate, voided volume and PVR from baseline to 1 month after the treatment day.

Voiding frequency at daytime and nighttime is measured as mean of the three-day voiding diary preceding the scheduled visit and the record days are 3 days.

Net change of each efficacy item will be analyzed by paired t-test between baseline and post-treatment in the treatment group and controlled group. The net changes of each efficacy item will be analyzed by ANOVA test to compare between treatment group and controlled groups. The global response assessment by the patients will be analyzed by Fisher exact test between the treatment and controlled groups.

All efficacy variables will be reported of respective point estimated and 95% confidence interval. Comparison tests will be reported of respective p value.

Secondary Safety Endpoints

- (1) Local adverse event incidences (hematuria, micturition pain, UTI, urinary retention) will be reported by both treatment group and controlled group and by physiological systems as appropriate. Incidence of adverse events and the categories of adverse event severity between treatments will be analyzed. The coding system used will be COSTART.

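### The default in Protocol 6.1 that treats doubtful deterioration as lack of efficacy may under-count pain on voiding, a named safety endpoint, in both arms

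*Protocol*

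**What the plan says.** Protocol 6.1 opens with a broad definition: "An adverse event is defined as a new medical condition or worsening of the existing condition". It then recognises that some deterioration could be either an adverse event or a sign that treatment has not worked, and settles those cases by default: "Situations as such should be considered as a lack of efficacy unless the sponsor or the investigators or the regulatory authorities state to the contrary".

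Protocol 2 names four local safety events: hematuria, pain on voiding, UTI and urinary retention. SAP 7.2 repeats them: "Local adverse event incidences (hematuria, micturition pain, UTI, urinary retention) will be reported by both treatment group and controlled group". It adds a comparison: "Incidence of adverse events and the categories of adverse event severity between treatments will be analyzed".

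The entry criteria in Protocol 4.2 require bladder-related discomfort: "Patients with symptoms of unpleasant sensation (pain, pressure, discomfort) perceived to be related to the urinary bladder". Neither document exempts the four named events from the default, gives criteria for overriding it, or asks for a list of the cases settled by it.

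**The concern.** The default works against the definition just before it. A worsening is an adverse event by definition, but a worsening of uncertain origin is not, unless someone says so. In a painful bladder condition, a flare of pain on voiding in the days after a session can plausibly be read either way. If nobody intervenes, it is classed as treatment failure and need not reach an Adverse Event Form.

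Safety is half of the stated objective, and pain on voiding is one of only four local events chosen to measure it. Events lost in this way would lower the reported incidence in each arm and narrow any true difference between arms. Because defaulted cases are not listed, a reader of the results could not tell how many there had been.

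**Working it through.** The documents give no adverse event rate, no expected share of doubtful events and no power for safety, so there is no figure to reproduce. The check has two parts.

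**1. Which named events are exposed to the default?**

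- *Pain on voiding:* exposed. Bladder pain is an entry symptom (Protocol 4.2). IC-related medication is stopped at screening (5.2.1.11) and several pain medicines are prohibited (5.4), so worsening has a rival explanation in either arm. Section 5.1 asks about pain during the session, which does not cover a flare afterwards. The item lists for V2 to V4 (5.2.3 to 5.2.5) do not mention adverse events, which first appear as an item at V5. However, 5.1 mentions adverse event recording at the treatment visit, and 6.1 requires all events to be documented.
- *Urinary retention:* weakly exposed. Protocol 4.3 excludes "Patients with PVR >100 ml" and also excludes outlet obstruction, so retention on study would usually be a new condition. PVR is measured at V5, V6 and V7 in any case.
- *Hematuria and UTI:* little exposed. Neither is readily read as lack of efficacy.

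**2. What would equal loss in both arms do?**

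Inputs: n = 25 per arm (SAP 7.4), so one patient is 1/25 = 4 percentage points. The true rates p and the absorbed share f are assumptions. The same f is used in both arms, because the rule is common and the patient and the investigator or follow-up observer are blinded (Protocol 3.2).

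- Expected events lost per arm = 25 × p × f
- Recorded risk difference = (p_LESW − p_placebo) × (1 − f)
- Recorded risk ratio = p_LESW(1 − f) / [p_placebo(1 − f)] = p_LESW / p_placebo, so unchanged

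For example, with 30% vs 10% and f = 0.50, losses are 25 × 0.30 × 0.50 = 3.75 and 25 × 0.10 × 0.50 = 1.25. The risk difference is 0.20 × 0.50 = 0.10.

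| Assumed true rates, LESW vs placebo | f | Lost, LESW | Lost, placebo | Recorded risk difference (points) |
|---|---|---|---|---|
| 30% vs 10% | 0 | 0 | 0 | 20 |
| | 0.25 | 1.875 | 0.625 | 15 |
| | 0.50 | 3.75 | 1.25 | 10 |
| | 0.75 | 5.625 | 1.875 | 5 |
| 20% vs 20% | 0.50 | 2.5 | 2.5 | 0 |
| 10% vs 20% | 0 | 0 | 0 | −10 |
| | 0.50 | 1.25 | 2.5 | −5 |

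A true difference in either direction shrinks towards zero, and no difference stays no difference. Which arm loses more events depends entirely on the true rates.

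Within one arm, an assumed 5/25 (20%, exact 95% limits 7% to 41%) that became 2/25 would be reported as 8% (1% to 26%).

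**The case against.** The strongest reply is that the default is narrow. It applies only where the cause is in doubt, and the investigators can override it on their own authority. Both documents list pain on voiding under local adverse events, and that specific listing can fairly be read as prevailing over a general rule. Worsening is not lost from the data either: VAS, O'Leary-Sant score and GRA are recorded at V5 to V7, and GRA runs down to markedly worse. If the comparison is made as a risk ratio, equal loss leaves its expected value unchanged.

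Much of this stands. It means that under-counting is possible rather than certain, and that the point is confined in practice to pain on voiding. It does not remove the point. The documents do not say which rule prevails, and the override has no criteria and depends on someone acting. A flare after an early session may resolve before V5. The scores do not count pain on voiding as an event. An unchanged risk ratio would still rest on fewer events, and each arm's reported incidence would still be too low.

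A reader might also infer that the loss would fall mainly on LESW, because irritation from the shock waves would occur there. The documents do not support this. One rule applies to both arms under blinding, medication is withdrawn in both, and SAP 7.4 itself assumes less improvement on placebo (5.0 against 8.0 points). Doubtful deterioration could therefore be as common there, or more so. Greater loss under LESW follows only if LESW truly causes more such events, or if f differs by arm, and neither is documented.

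**Conclusion.** The point holds in a limited form. The default in 6.1 may under-count pain on voiding in both arms, and so reduce any real between-arm difference in risk by the share of events absorbed. The other three named events are little affected, and the documents give no ground for expecting more loss in one arm.

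The size cannot be fixed from the documents. Under the assumed rates of 30% and 10%, a 20-point difference falls to between 15 and 5 points as f runs from 0.25 to 0.75. These figures rest on assumed rates, equal f in both arms and at most one counted event per patient. They show the mechanism and do not predict the trial's result. The change is a cheap improvement to the recording rule. The point does not bear on the primary analysis.

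**What to change.** Add one sentence to Protocol 6.1, for example:

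*Any new or worsened hematuria, pain on voiding, UTI or urinary retention after the first session is recorded on an Adverse Event Form, with a relatedness judgement made blind to allocation, whether or not it may also reflect lack of efficacy.*

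The default may stay for other deterioration, which VAS, O'Leary-Sant score and GRA capture at V5 to V7. The sentence should not be widened to bladder pain in general. That is not one of the four named events, it overlaps with the efficacy outcomes, and after medication is stopped it could bring many disease flares into adverse event reporting.

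The cost is some additional forms and the reporting that goes with them. Event counts would rise somewhat in both arms because ordinary disease fluctuation is included, and the blinded placebo arm shows how much of the count is background. No treatment, visit or efficacy analysis changes.

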6.2. Nonserious Adverse Event

A nonserious adverse event is defined as a change in a patient's medical health which does not fulfill the definition of Serious Adverse Event. Nonserious AEs should be reported to ADR by use of an Adverse Event Form.

6.3. Serious Adverse Event

Serious adverse events are defined as any finding which suggests a significant hazard, contraindication, side effect, or precaution.

Additionally, any adverse event which the consequence is:

Fatal

Life threatening

Permanently disability or incapacity

Requiring hospitalization or prolonging a current hospitalization

A congenital abnormality

Serious, alarming and/or unusual adverse events must be reported to the following individual within 24 hours of the investigator's knowledge of the event.

An Adverse Event Form should be completed for all serious adverse events and forwarded to the ADR within 24 hours. When new significant information is obtained as well as when outcome of an event is known, the investigator should inform the ADR. In applicable cases, ADR may request a letter from the investigator summarizing events related to the case. Investigators should follow patients as far as possible until an outcome to the events is known.

The investigator is responsible to communicate details of medical emergencies in trial patients to the ethics Committee.

REFERENCES

7. STATISTICAL ANALYSIS

7.1. Evaluability

Patients receiving baseline screening and treatment will be considered as intent-to-treat (ITT) population. The ITT population with the following conditions will be considered as per-protocol (PP) population:

- 1. Not taking any prohibited medications
- 2. Fulfilling all entry criteria
- 3. Have treatment visit and post-treatment evaluations on the primary endpoint

The efficacy evaluation will be performed on both the ITT and PP datasets while the safety evaluations will be performed only on the ITT datasets. The primary conclusions will be made for the primary and secondary endpoints on the ITT patients.

7.2 Analysis

The statistical objective of this study is to demonstrate that the efficacy of LESW is superior to placebo with respect to the decreases of O'Leary-Sant symptom score, VAS, increase in functional bladder capacity and improvement in GRA. The safety profile of LESW or placebo for the either group of intravesical treatment of patients with IC/BPS will also be confirmed.

Primary Efficacy Endpoint

The efficacy of LESW treatment will be evaluated for:

(1) Net change of the O'Leary-Sant symptom score from baseline to 1 month after the treatment day.

Secondary Efficacy Endpoint

The efficacy of LESW will be evaluated for:

- (1)Net change of the following parameters from baseline to 1 month after the treatment day: Visual analog score (VAS) for pain (from 0 to 10), functional bladder capacity (FBC), voiding frequency at daytime and voiding frequency at night time as recorded in 3-day voiding diary.
- (2) Global response assessment (GRA) of satisfaction by the patient (categorized into -3, -2, -1, 0, 1, 2, 3, indicating markedly worse to markedly improved) at 1 month after the treatment day. An improvement of GRA by 2 scales at 1 month is considered effective.
- (3) Net changes of the maximum flow rate, voided volume and PVR from baseline to 1 month after the treatment day.

Voiding frequency at daytime and nighttime is measured as mean of the three-day voiding diary preceding the scheduled visit and the record days are 3 days.

Net change of each efficacy item will be analyzed by paired t-test between baseline and post-treatment in the treatment group and controlled group. The net changes of each efficacy item will be analyzed by ANOVA test to compare between treatment group and controlled groups. The global response assessment by the patients will be analyzed by Fisher exact test between the treatment and controlled groups.

All efficacy variables will be reported of respective point estimated and 95% confidence interval. Comparison tests will be reported of respective p value.

Secondary Safety Endpoints

- (1) Local adverse event incidences (hematuria, micturition pain, UTI, urinary retention) will be reported by both treatment group and controlled group and by physiological systems as appropriate. Incidence of adverse events and the categories of adverse event severity between treatments will be analyzed. The coding system used will be COSTART.
- (2) The abnormalities of laboratory test results will be reported by patient list in the patients who have been tested for having severe adverse event.
- (3) The changes in physical examinations will be presented in the by-patient list.
- (4) All statistical tests used will be two-tailed with α = 0.05.

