7.4 Sample Size

The sample size per treatment group is arbitrarily determined to be 25 evaluable patients within the two-year study period. Approximately 50 patients are planned to be enrolled to complete the study.

The design of this study was compared between the two groups. The main evaluation index (O'Leary-Sant score) was set to 8.0 decreased in the treatment group, 5.0 decreased in the control group, SD = 5.0, α = 0.05, power= 0.80, and the total sample size was analyzed by computer:

The sample size of this study is about 25 people in each group, at least 50 people need to reach statistical significance.

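### The SAP aims to show superiority on four outcomes but has no rule tying claims on VAS, bladder capacity or GRA to the O'Leary-Sant primary

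*SAP*

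**What the plan says.** The statistical objective in SAP 7.2 is to demonstrate that LESW is "superior to placebo with respect to the decreases of O'Leary-Sant symptom score, VAS, increase in functional bladder capacity and improvement in GRA". The sentence names four outcomes and does not rank them.

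The ranking comes from the endpoint lists. SAP 7.2 gives one primary endpoint: "Net change of the O'Leary-Sant symptom score from baseline to 1 month after the treatment day". VAS, FBC and GRA are listed as secondary. SAP 7.4 sizes the trial on the primary alone: "The main evaluation index (O'Leary-Sant score) was set to 8.0 decreased in the treatment group, 5.0 decreased in the control group, SD = 5.0".

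The rules for testing and concluding do not carry that ranking through:

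- Level: "All statistical tests used will be two-tailed with α = 0.05".
- Continuous outcomes are compared between groups by ANOVA. For GRA: "The global response assessment by the patients will be analyzed by Fisher exact test between the treatment and controlled groups".
- Conclusions (SAP 7.1): "The primary conclusions will be made for the primary and secondary endpoints on the ITT patients".

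Neither document contains a testing order, a gate, a multiplicity adjustment, a statement that the secondaries are supportive, or a definition of trial success.

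The GRA endpoint also has two time points. SAP 7.2 says: "An improvement of GRA by 2 scales at 1 month is considered effective". The secondary-endpoint list in Protocol section 2 has GRA "indicating markedly worse to markedly improved) at 3 months after the treatment day".

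**The concern.** When an objective names several outcomes and gives each a full 5% test, the reader needs to know what counts as success. Here two readings are possible. If all four outcomes must be significant, the rule is strict and false claims are rarer than for the primary alone. If any one of the four can carry a superiority claim, having a single primary no longer limits the overall chance of a false claim, because VAS, FBC or GRA could be put forward after O'Leary-Sant had failed.

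The text does not choose between these readings. Left open until after unblinding, the choice could follow the results.

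A failed primary is also a realistic outcome. On the inputs in SAP 7.4, the planned 25 per group give the primary test power of 54.7% rather than 80%. That shortfall is a separate matter. It is relevant here only because it makes the unregulated situation likely to arise.

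**Working it through.** **The plan's own figure.** The documents state no overall error rate, so there is none to reproduce. The only related figure is the sample size in SAP 7.4, which bears on how often the primary would fail. Its inputs are a difference of 8.0 − 5.0 = 3.0 and SD 5.0, so d = 3.0/5.0 = 0.6, with two-sided α = 0.05 and power 0.80. A two-sample t-test then needs 45 per group (44 by the normal approximation), not 25. Power at 25 per group is 0.547, so the primary would miss significance with probability 1 − 0.547 = 0.453 even if the assumed effect is real.

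**Inputs for the error rate.**

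- From SAP 7.2: four outcomes (O'Leary-Sant, VAS, FBC, GRA), each tested at two-sided 0.05, which is 0.025 in the direction favouring LESW.
- From SAP 7.4: 25 per group, used for the Fisher calculation.
- Assumed, because the documents give no values: a common correlation ρ of 0, 0.5 or 0.8 between the test statistics; a GRA responder rate of 20–50%, the same in both arms; and Fisher's test applied to responder yes/no rather than to the seven GRA categories.

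**Step 1: any false claim favouring LESW, on the any-one reading, with no true effect on any outcome.** For independent tests this is 1 − 0.975⁴ = 0.0963. For equicorrelated normal statistics, numerical integration gives 0.0779 at ρ = 0.5 and 0.0571 at ρ = 0.8.

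**Step 2: the event at issue.** The totals in step 1 include the 0.025 that belongs legitimately to the primary. The chance that the primary does not favour LESW significantly but at least one of the other three does is the total minus 0.025:

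- ρ = 0: 0.0963 − 0.025 = 0.0713
- ρ = 0.5: 0.0779 − 0.025 = 0.0529
- ρ = 0.8: 0.0571 − 0.025 = 0.0321

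**Step 3: allowing for Fisher's test on GRA.** With 25 per arm, the exact chance of p < 0.05 favouring LESW is 0.0111, 0.0114, 0.0148 and 0.0164 at responder rates of 20, 30, 40 and 50%. Using these for GRA, with 0.025 for the other three outcomes, gives totals of 0.0834–0.0884, 0.0686–0.0721 and 0.0511–0.0531 at the three correlations. Subtracting 0.025 again gives the third column below.

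| ρ (assumed) | Primary fails, at least one of three falsely favours LESW | Same, with Fisher on GRA | All four must succeed |
|---|---|---|---|
| 0 | 7.1% | 5.8–6.3% | <0.01% |
| 0.5 | 5.3% | 4.4–4.7% | 0.07% |
| 0.8 | 3.2% | 2.6–2.8% | 0.52% |

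**Step 4: with a fixed sequence behind the primary.** A claim after a failed primary is excluded, so the second and third columns become 0. The chance of any false claim favouring LESW when there are no true effects is 2.5% at every correlation.

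A gate on the primary with no order behind it would be weaker. If the primary effect is real and the three secondaries have no effect and are independent, the chance of at least one false positive among them is up to 1 − 0.95³ = 0.143 two-sided. The fixed order prevents this.

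**The case against.** The strongest reply is that the plan already has a hierarchy. One endpoint at one time point is called primary, the trial is sized on it, and the other three appear under a secondary heading. Nowhere do the documents say that one of the four is enough or that a secondary may stand in for a failed primary. The objective sentence joins the outcomes with *and*, which read literally asks for all four, and on that reading there is no inflation. The sentence in SAP 7.1 about primary conclusions mainly chooses the ITT population over per-protocol.

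Much of this stands. The primary's 5% level is untouched, and the error rates above apply only on the any-one reading. A reader might infer that the plan's overall false-positive rate is about 9.6%, or that the primary result is itself compromised. The documents support neither. The 9.6% needs the any-one reading and independence, which is the upper end of the assumed range, and it includes the primary's own 2.5%.

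The reply does not close the gap. The SAP makes superiority on VAS, FBC and GRA part of what the trial sets out to demonstrate, gives each a full-level test, and names primary and secondary endpoints together when it says where conclusions are drawn. A label alone does not stop a confirmatory claim on one of the three after a failed primary.

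A reader might also infer that claims on the remaining secondaries or on per-protocol results should be barred. They are not in the objective sentence, no error has been shown for them, and SAP 7.1 and 7.2 already place conclusions on ITT and require estimates with 95% confidence intervals.

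**Conclusion.** The concern holds in a limited form and should be fixed. Followed as written, the plan does not rule out a superiority claim on VAS, FBC or GRA after a non-significant O'Leary-Sant result.

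On the any-one reading, with no true effects, the extra chance of a false claim for LESW runs from about 7% (independent outcomes) down to about 3% (correlation 0.8). With Fisher's test on GRA it runs from about 6% down to just under 3%. These figures rest on assumed correlations and responder rates and on a responder yes/no GRA test. On the all-four reading there is no inflation. The gap does not alter the primary test, its estimate or the sample size.

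The GRA time point is a direct contradiction between the documents: 3 months in the Protocol's secondary endpoints and 1 month in the SAP. No rule can cover GRA until it is settled.

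**What to change.** State in SAP 7.1 and 7.2 that the trial's conclusion rests on the O'Leary-Sant change at 1 month in the ITT population. Then choose one of two options before unblinding:

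1. **Fixed sequence.** Test VAS, FBC and GRA for superiority only after a significant primary, in a prespecified order (the order in the objective sentence would do), each at two-sided 0.05, stopping at the first non-significant result.
2. **Supportive only.** Add one sentence saying that these three outcomes are supportive and carry no confirmatory claim.

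Under either option, reconcile the secondary GRA time point between Protocol section 2 and SAP 7.2, and state whether Fisher's test uses the responder definition, so that GRA has one defined test. Protocol 5.2.7 and 5.2.8 already record GRA at both 1 and 3 months, so neither choice of time point needs new data. No added restriction on the other secondaries or on per-protocol results is needed.

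The cost is a few sentences, with no change to the primary test or the sample size. The real downside is that no confirmatory claim on VAS, FBC or GRA is possible if the primary is not significant. On the SAP's own inputs that would happen about 45% of the time even if the assumed effect is real.
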